Appendix 11: Participant case record form

Participant details			
Name		UIN	
NHS no.		Hospital Site	
DOB	Age	Gender	Ethnicity
Address			
Screening questions			
Could you be pregnant (if applicable)?			
Do any of the following diagnostic categories apply to your past medical history? (please circle):			
HIV infection, diabetes, malignancy, autoimmune diseases, keloid scarring, any skin disease, allergy to local anaesthetic injection			
Do you take any of the following medication? (please circle):			
Anti-TNF, Corticosteroids, Azothioprine, Cyclosporin, FK506, Methotrexate, Tacrolimus			
Why were you referred to the TB clinic? (please circle):			
Recent TB contact, recent migration to the UK, occupational health screening, other			
Country of birth			
Date of entry to UK, if non-UK born			
If you have recently had contact with someone with TB, where was this? (please circle):			
Household, work, healthcare setting, transport, social contact, other			
If you have recently had contact with someone with TB, what was the date of the most recent contact?			
Have you been vaccinated with BCG? If so, what year was this?			
Have you been diagnosed with TB disease before? If so, what year was this?			
Have you recently had a tuberculin skin test done? If so, what date was this?			
Date of consent			
Pre-TST	Persistent cough for more than two weeks?		Continue 
Blood 	Weight loss in the last 3 months?		End study 
CXR 	Drenching night sweats during the last 3 months?		
Visit 1: Tuberculin skin test in each arm			
Lot number	Date	Administered by	Signed
Visit 2: Read TST induration, local anaesthetic, TST biopsy 1			
TST L induration	TST L photograph 	TST R induration	TST R photograph 
Lot Number (48hr)	Date	Administered by	Signed
TST biopsy 1 		Signed	
Visit 3: Local anaesthetic, TST biopsy 2			

Lot Number (Day 7)	Date	Administered by	Signed		
TST biopsy 2 		Signed			
Eligibility for cohort studies					
LTBI treatment study?	Yes 	No 	Longitudinal contact study?	Yes 	No 
Accepted and commenced LTBI treatment?				Yes 	No 

Longitudinal study follow up assessments (mark with tick or cross)			Outcome (circle)
3 months		Persistent cough for more than two weeks?	Continue Treatment study End study
Blood	Weight loss in the last 3 months?		
CXR	Drenching night sweats during the last 3 months?		
6 months		Persistent cough for more than two weeks?	Continue Treatment study End study
Blood	Weight loss in the last 3 months?		
CXR	Drenching night sweats during the last 3 months?		
9 months		Persistent cough for more than two weeks?	Continue Treatment study End study
Blood	Weight in the last 3 months?		
CXR	Drenching night sweats during the last 3 months?		
12 months		Persistent cough for more than two weeks?	Continue Treatment study End study
Blood	Weight loss in the last 3 months?		
CXR	Drenching night sweats during the last 3 months?		
15 months		Persistent cough for more than two weeks?	Continue Treatment study End study
Blood	Weight loss in the last 3 months?		
CXR	Drenching night sweats during the last 3 months?		
18 months		Persistent cough for more than two weeks?	Continue Treatment study End study
Blood	Weight loss in the last 3 months?		
CXR	Drenching night sweats during the last 3 months?		
21 months		Persistent cough for more than two weeks?	Continue Treatment study End study
Blood	Weight loss in the last 3 months?		
CXR	Drenching night sweats during the last 3 months?		
24 months		Persistent cough for more than two weeks?	Continue Treatment study End study
Blood	Weight loss in the last 3 months?		
CXR	Drenching night sweats during the last 3 months?		
Notes			

LTBI treatment study follow up assessments (mark with tick or cross)				Outcome (circle)
4 weeks		Persistent cough for more than two weeks?		Continue End study
Blood		Weight loss in the last 3 months?		
		Drenching night sweats during the last 3 months?		
Missed doses in last 4 weeks?			Pill count?	
8 weeks		Persistent cough for more than two weeks?		Continue End study
Blood		Weight loss in the last 3 months?		
		Drenching night sweats during the last 3 months?		
Missed doses in last 4 weeks?			Pill count?	
12 weeks		Persistent cough for more than two weeks?		Continue End study
Blood		Weight in the last 3 months?		
		Drenching night sweats during the last 3 months?		
Missed doses in last 4 weeks?			Pill count?	
24 weeks		Persistent cough for more than two weeks?		Continue End study
Blood		Weight loss in the last 3 months?		
		Drenching night sweats during the last 3 months?		
Missed doses in last 4 weeks?			Pill count?	
Notes

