The longitudinal study will recruit individuals with LTBI from the existing UK contact screening program^{11,27}. The additional individuals for the cross-sectional study will be recruited from the Public Health New migrant screening program referrals to LTBI clinics. Clinical staff at each participating site (Appendix 1) will introduce potentially eligible individuals (Section 7) to the study team, who will seek to obtain informed written consent (see Section 6). The study schedule for participants who give consent is summarised in Appendix 2. They will undergo a chest radiograph (provided by the routine NHS Trust clinical service) and screening blood tests (Appendix 3) and, followed by one tuberculin skin test in each arm. One TST site will be biopsied at 48 hours and the second TST site will be biopsied at seven days (Appendix 4). All blood tests, chest radiography, TSTs and biopsies will be performed within the TB clinic the participant was recruited from.

Participants who have a positive blood transcriptional biomarker will then enter the LTBI treatment sub-study. In the absence of clinical evidence of active TB, they will be offered LTBI therapy as part of their usual NHS care, and asked to attend appointments after 4, 8, 12 and 24 weeks for clinical review and repeat blood sampling (the 4, 8 and 12 week time points are aligned with those required in routine clinical care for monitoring). Adherence to LTBI therapy will be measured by self-report questionnaire, pill counts, urine testing and/or medication boxes, depending on local site availability and practice.

Participants with a negative blood transcriptional biomarker and who meet the eligibility criteria for the longitudinal study will be asked to attend follow up clinic appointments with the study team at three monthly intervals for two years. These additional appointments will take place at the TB clinic the participant was recruited from. At each appointment they will complete a questionnaire (Appendix 5), undergo blood sampling

and a chest radiograph. Participants can withdraw at any time without giving a reason. Participants will also be consented for recall by selected genotype or phenotype to obtain additional peripheral blood samples within the five-year lifetime of this study for in vitro mechanistic studies (see secondary objectives).

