9.1. Sample size and statistical power

We will recruit 400 LTBI contacts of active pulmonary TB cases to address the primary objective. This sample size is derived from estimated progression from LTBI to active TB within 2 years of 5%, giving 20 progressors and 380 non-progressors. Progressive disease may be due to a range of different immune responses, and each variation may only be evident in a subset of cases. Therefore, conventional differential gene expression analysis in the TST between groups of progressors and non-progressors, may not identify statistically significant differences. Instead, we will undertake supervised outlier profile analysis to identify gene expression among subsets of progressors, which lies outside the normal range measured in non-progressors. These methods provide robust statistical confidence by incorporating multiple testing corrections³²⁻³⁶, and have been successfully applied to discovery of novel oncogenic pathways^{32,37}. Using preliminary TST transcriptomic data from HIV negative individuals in computational simulations, we estimate >0.8 statistical power in this sample size to detect significant outlier traits among progressors (false discovery rate <0.05) when the outlier trait is shared by 5 or more progressors (Figure 2A). In order to identify eQTLs of TST transcriptomic data, we estimate that a sample size of 1000 is required to give >90% power to detect statistically significant correlations ($p < 10^{-8}$) for allelic frequencies $\geq 5\%$ depending on the correlation coefficients, as a composite measure of effect size and variance⁶¹. Finally, from our pilot data, we estimate that 15% of these individuals will express the blood transcriptional biomarker at time of recruitment to the study. Of these estimated 150 participants, 80 will be recruited to the LTBI treatment sub-study. Conservatively assuming that only 25% of patients decline LTBI therapy, a sample size of 68 participants will provide 80% power to detect a difference of 0.8 standard deviations (SDs) in signature scores between those who accept and decline treatment at each time point. This calculation assumes similar standard deviations among individuals in both groups. We have estimated 0.8SDs as the minimum difference in signature scores that is likely to be of clinical significance (based on the difference in mean scores between IGRA-positive and IGRA-negative TB case-contacts in our pilot data. To allow for losses to follow-up, 80 participants will be recruited.

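### The case record form (CRF) records where and when contact took place but not with which index case, so the comparison of progressors with non-progressors cannot fully allow for shared exposure

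*Protocol*

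**What the plan says.** **Recruitment.** Protocol Section 5 states: "The longitudinal study will recruit individuals with LTBI from the existing UK contact screening program". Section 7.1 requires contact with a new pulmonary case. Neither section limits entry to one contact per index case or household.

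**Data collected.** Appendix 11 asks "If you have recently had contact with someone with TB, where was this? (please circle", with household as the first option, and then the date of the most recent contact. It has no index-case number, no household number and no field for a participant's relation to other participants. It does record address, NHS number and hospital site.

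**Linkage.** Under Section 12.1 the study data are keyed by UIN alone. Under Section 12.3 the UIN is separated from the identifying information at the end of the study.

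**Primary analysis.** Section 9.1 says "We will recruit 400 LTBI contacts of active pulmonary TB cases to address the primary objective" and bases the size on "estimated progression from LTBI to active TB within 2 years of 5%, giving 20 progressors and 380 non-progressors". It claims power above 0.8 for finding outlier traits in this cohort. The error criterion is given as "false discovery rate <0.05", and the power is claimed for the case "when the outlier trait is shared by 5 or more progressors". Section 9.2 adds a comparison of co-correlated gene clusters between progressors and non-progressors. Neither section mentions index case, household or relatedness.

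**The concern.** People exposed to the same index case share the strain and the timing of exposure, and may share intensity of exposure, home and genes. Section 2 of the protocol accepts that TB risk has a host genetic component and expects genotype to influence the skin-test response. On the protocol's own premises, members of one exposure group may therefore resemble each other in both quantities that the primary analysis relates.

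Several progressors from one index case who show the same unusual expression are weaker evidence of a general risk trait than the same number from separate index cases. An analysis can allow for this only if it knows who shares an index case. A later statistical analysis plan can choose a method, but it cannot supply a grouping variable that was never collected. That makes this a point about the protocol and its CRF.

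**Working it through.** **1. The plan's own figures.** 400 × 0.05 = 20 progressors and 400 − 20 = 380 non-progressors, as Section 9.1 states. The power above 0.8 cannot be reproduced, because it comes from simulations on preliminary data shown in Figure 2A, which is not available.

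**2. What the study's data can link.**
- Same household: yes, through the address, until the UIN is unlinked.
- Blood relatives: yes, through the genome-wide genotypes planned for all 1000 participants (Section 9.2).
- Same index case, different household, unrelated (for example contacts at work, in transport or socially): no. Site, setting and date may narrow the possibilities but do not identify the index case.

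**3. Reference probability with unrelated progressors.** Take as an outlier an expression value above the 99th percentile of non-progressors (an assumption). The chance that at least 5 of 20 progressors exceed it for a gene with no true effect is

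P = Σ (k = 5 to 20) C(20,k) × 0.01^k × 0.99^(20−k) = 1.37 × 10⁻⁶.

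This shows sensitivity to grouping. It is not the error rate of the planned procedure.

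**4. The same probability with exposure groups.** All inputs here are assumptions.
- Expression: X = √ρ·U + √(1−ρ)·e, with U common to the group and ρ = 0.3 or 0.5. Given U = u, the outlier probability is Φ((√ρ·u − 2.326)/√(1−ρ)). The group counts are averaged over U and added across groups.
- Enrolment: all 400 in pairs, or all 400 in fours.
- Outcome: progression in 5%, with correlation r in an underlying normal liability. Only cohorts with exactly 20 progressors are kept (3,000 per setting).

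| Enrolled in | r | Progressors (of 20) sharing a group with another progressor, mean | Ratio to 1.37 × 10⁻⁶, ρ = 0.3 | ρ = 0.5 |
|---|---|---|---|---|
| pairs | 0 | 0.9 | 1.1 | 1.3 |
| pairs | 0.2 | 2.0 | 1.2 | 1.6 |
| fours | 0 | 2.8 | 1.4 | 2.1 |
| fours | 0.2 | 5.2 | 1.9 | 4.1 |

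The range is about 1.1 to 4. If 40,000 gene-tails were examined (also an assumption), expected false shared traits would go from 40,000 × 1.37 × 10⁻⁶ = 0.05 to between 0.06 (× 1.1) and 0.22 (× 4.1).

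**5. Sensitivity to the outcome scale.** A correlation of 0.2 between the yes/no outcomes themselves is far stronger clustering than 0.2 in liability. In fours it places on average 9.7 of the 20 progressors in a group with another progressor, and the ratio is 3.7 (ρ = 0.3) to 13 (ρ = 0.5). In pairs it is at most 2.6.

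**6. Effective number of progressors.** With group sizes mᵢ, the effective number is 20 / (1 + (Σmᵢ²/20 − 1)·ρ). For one triple, one pair and 15 singles, Σmᵢ² = 9 + 4 + 15 = 28. This gives 20/1.12 = 17.9 at ρ = 0.3 and 20/1.20 = 16.7 at ρ = 0.5.

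**The case against.** **Much of the grouping is recoverable.** The address identifies shared homes while identifiers are still linked, and genotypes identify relatives. The unlinkable remainder shares neither home nor genes, so the case for similar expression is weakest there. This stands, and it narrows the gap to the index-case link and to having a household code ready in the UIN-keyed data. It does not close the gap, because the remainder still shares strain and timing of exposure.

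**Independence is not stated.** The protocol nowhere says that progressors are treated as independent. That is inferred from silence, and the handling could be in a statistical analysis plan or in the unseen simulation. This also stands, but any such handling needs a variable that the CRF does not collect.

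**Stronger readings that the documents do not support:**
- A reader might take five progressors as a rule for declaring a trait, so that one family could produce a finding. In Section 9.1 the five is the condition under which power exceeds 0.8, and the error criterion is the false discovery rate. One family reaching five would also have to supply 5/20 = 25% of all expected progressors.
- A reader might put all 20 progressors into ten pairs or five groups of four, which gives ratios of 4 to 11 and 28 to 156. At 5% progression that layout is not credible. It arose in none of the simulated cohorts, even with outcome correlation 0.2 on either scale.
- A reader might extend the point to the eQTL analysis. Relatedness there can be estimated from the genotypes, needs no new data, and may be left to the analysis plan.

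**An offset.** Non-progressors from the same groups can carry the same expression and widen the normal range. The calculation holds the cut-off fixed and ignores this.

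**Conclusion.** The point holds as a gap in data collection. Contacts of one index case can enrol together, and those who neither live together nor are related cannot be linked from the study's data. The outlier and gene-cluster comparisons therefore cannot fully allow for shared exposure.

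The likely size is modest: roughly a 1.1- to 4-fold rise in the chance of a false shared outlier trait under the liability-scale assumptions above. It would reach about 13-fold only with fours and outcome clustering strong enough to group about half of the progressors. Group sizes, correlations and cut-off are assumptions, since the protocol supplies none of them. The documents do not show that the false discovery rate of the planned analysis is materially understated. They show that the question could not be fully checked afterwards. Because the remedy is cheap and must come before identifiers are unlinked, the change should be made.

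**What to change.** - Add two fields to Appendix 11: a pseudonymised index-case code and a household code. Take both from the contact-tracing record, link them to the UIN, and keep them in the analysis data after unlinking. For participants already enrolled, complete them while identifiers are still linked.
- When obtaining outlier p-values, permute outcome in a way that respects index-case blocks.
- For each reported outlier trait, state how many distinct index cases its progressors come from.

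Cost: two extra fields, access to the contact-tracing record, and a slightly smaller effective number of progressors (for example 17 to 18 rather than 20 in the illustration above), so slightly less favourable power than Section 9.1 suggests.
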